pulsing manner TPMS that encompass previously employed range of frequencies in humans for pelvic floor stimulation (based on published methodology -Lim et al, J Urol 197:1302, 2017, attached). Number of trains will be about 50. no of pulses in train would be about 240. Each cycle will be of total 20 minutes duration, followed by 20 min of coil cooling period before the second cycle. Based on our preliminary studies in 2 subjects for about 8 weeks, this protocol was well toleated. Both subjects felt the sensations at the high frequency 30 Hz. Same TPMS device will be used for the control (G1: sham) group, but with a sham magnetic coil. Sham coil is designed to provide <5% energy during sham TPMS. The treatment regimen will involve two 20minute sessions/visit and 2 -visits per week as follows: Weeks: 1, 2, 3, 4, 5, 6, 7, 8, 9, 10, 11, 12 (final monitoring at 24 weeks). TPMS will be administered by a trained clinical coordinator under the supervision of an urologist. The coordinator will not be involved in subject's assessment. We will apply first low amplitude (5%) to improve blood flow followed by high amplitude (30-50 %) TPMS, to strengthen muscles. Symptom scoring using questionarries and blood flow (Doppler) will be perfored at: baseline (before starting TPMS), and at weeks 4,8, 13, 24 after starting TPMS as shown in the atatched figure: IRB Methods: Timeline. At the initial visit, subjects will receive education about TPMS and anatomy and the role of TPMS in increasing pelvic blood flow and muscle strength. This protocol will allow us to quantify the direct beneficial effect of TPMS on muscle strengthening. Patients will also get standard clinical care and training for pelvic floor exercise.

Chair & Parameters Used: The coil will be placed on a chair manufactured by MagVenture with additional sponge to make the coil comfortable to sit on. This coil will be energized to provide magnetic stimulation at the identified amplitude, frequency and duration. The magnetic field generated during stimulation will subsquently stimulate the tissue in its field. Data Analysis & Interpretation:

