Data Analysis & Interpretation: We will analyze qualitative interview data using atlas.ti, qualitative data analysis software, and the quantitative data using the SPSS version 24. We will start by coding, a process in which quotes are marked and labeled. The labeled quotes are then sorted and grouped, so that categories, then concepts, then themes can be developed. As is often standard practice for qualitative data analysis, analysis will be concurrent with data acquisition. Quantitative data will be examined initially for missing values. The primary aims of our data analytic strategy will be directed toward the adherence, retention and any guidance to inform modification of our method. We will focus our analyses on a feasibility of conducting a larger study and report our findings with this limitation in mind. Our goal is to collect important data regarding our method, our ability to implement recruitment strategies, and the feasibility of the treatment and measurements. Information derived from our research will lead to better-designed full-scale studies and informed decisions regarding whether it is worthwhile to commit additional resources to future treatment development. For quantitative data, descriptive statistics will be used to summarize the variables as well as detect outliers and data entry errors. When applicable, normality of the distribution will be examined for outcome variables. Chi-squared and Analysis of Variance will be used to assess the effectiveness of the randomization procedures by comparing participants in each treatment condition on baseline variables. Due to our small sample size our statistical analytical finding will be interpreted with caution. Other preliminary analyses will include evaluation of patterns of missing data, dropout rates, distributional properties of variables, and correlations among measures. Although there are important limitations associated with the analysis of our data, we do propose to conduct limited statistical analyses. First, keeping in mind the theoretical and practical issues reviewed above, all analyses will be considered preliminary. We will calculate an estimated effect size for our primary outcome, though it will be interpreted with caution, and in the context of the 95% confidence interval that surrounds it. It will also be interpreted within the context of other important information such as the clinical significance of study findings, and existing data from prior relevant research studies. For aims 2-3, All potential covariates (e.g., age, duration of cancer) will be summarized with descriptive statistics and graphs to determine whether a continuous, categorical, or interval representation is most appropriate. Second, effect of any systematic differences between dropouts and completers will be explored by including the variable of concern to the model as a covariate. Third, any comparison can be adjusted for subject-specific characteristics (e.g., covariates found in initial analyses). Furthermore, group by time interaction will be included in all models. For Aim 2-3, descriptive statistics and exploratory graphing such as frequencies, means, standard deviations, box and whisker plots, stem and leaf diagrams, and scatter plots will be used to assess normality of the data. If necessary, the continuous outcome data will be transformed appropriately. Prior experience leads us to expect that for all variables, the distributions will be skewed and the variances will not be homogeneous. Similarly, potential covariates will be summarized with descriptive statistics and graphs to determine whether a continuous, categorical or an interval representation is the most appropriate approach. Missing data will be examined to assess randomness. Analysis of variance will be used to test our hypothesis. We will adjust pvalues for multiple testing using a Bonferroni correction. Data will be analyzed using a Mixed Effect Model. This method allows the inclusion of subjects with missing data or those who terminated early without relying on data imputation procedures. Denominator degrees of freedom will be calculated using the Kenward-Roger small sample correction. Data will be analyzed from all randomized subjects for whom we have a baseline assessment and at least one post-baseline evaluation. Effect of these mediator variables will be tested using the same mixed model. To test for mediation effect, we will utilize the analytic strategy. The multiple-mediation model includes a multiple-path mediating effect through both mediators which allows one mediator to causally affect the other. We will conduct a Sobel testnto check for significant mediation. Next, we will use the formula provided by MacKinnon to determine the percentage of the intervention condition to primary outcome path that was accounted for by change in our mediator. Based on our ongoing studies, we expect a dropout rate of <10% after baseline assessment. Primary outcomes will be tested using an intent-to-treat framework. The data will be analyzed by a "Mixed Effect Model." As we mentioned above, due to our small sample size our statistical analytical finding will be interpreted with caution.

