### **Section 9.8 Questionnaires & Surveys**

9.8) Provide the name and a reference for questionnaires/surveys that are standard or identify them here and attach a copy of the questionnaire/survey. Questionnaires or surveys that are not clinical standard references must be uploaded. Reference the help link for additional information related to surveys administered to VA personnel and approved platforms for web-based surveys.

Primary symptom scores will be assessed using International Index of Erectile Function (IIEF-5) and International Consultation of Incontinence Questionnaire (ICIQ) symptom scores. Both of these questionnaires will take about 15-20 minutes to answer. Both questionnaires will be given in hard copy only. Electronic copies of these questionnaire have been attached to the application.

9.9) Provide a Data Safety Monitoring Plan (DSMP) or the details of a Data Safety Monitoring Board; if a written plan is available, attach a copy of the plan to the submission form.

This is a feasibility study using an non-invasive, previously FDA approved device. We will monitor for any adverse effects and report these to the IRB within 5 days following the guidelines provided in our internal policy (SOP Document 67) -Adverse event /unanticipated outcome. Local Research Deaths. We ensure oral notification of the Institutional Review Board (IRB) immediately upon becoming aware of any local research death that is both unanticipated and related to the research.

Local Serious Adverse Event (SAEs). We will ensure written notification of the IRB within 5 business days after becoming aware of any local SAE that is both unanticipated and related to the research.

Serious Problems. We will ensure written notification of the IRB within 5 business days after becoming aware of any serious problem that is both unanticipated and related to the research.

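### No treatment contrast is named and the baseline score is not listed as a covariate; one pre-named, baseline-adjusted contrast per symptom score would fix the test and gain precision at no cost in patients

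*Combined protocol and SAP*

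**What the plan says.** All modelling statements are in Section 9, under Data Analysis & Interpretation of the combined protocol and SAP.

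- Model: "Data will be analyzed using a Mixed Effect Model", with Kenward-Roger degrees of freedom. Also "Furthermore, group by time interaction will be included in all models".
- Test: "Analysis of variance will be used to test our hypothesis", and later "Primary outcomes will be tested using an intent-to-treat framework". Neither sentence gives a factor, visit or contrast.
- Multiplicity: "We will adjust pvalues for multiple testing using a Bonferroni correction". The number and identity of the tests are not given.
- Estimate: "We will calculate an estimated effect size for our primary outcome, though it will be interpreted with caution", read with its 95% confidence interval. The visit or average is not stated.
- Covariates: the examples are age and duration of cancer. The baseline score is not listed, and nothing says whether baseline enters as a response or as a covariate.

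Section 9, TPMS Treatment, schedules symptom scores and Doppler at "baseline (before starting TPMS), and at weeks 4,8, 13, 24 after starting TPMS". Section 9.8 names IIEF-5 and ICIQ as the primary symptom scores, without a visit. Section 9 also describes the work as feasibility-focused and every analysis as preliminary.

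**The concern.** A model with group, time and group-by-time offers several quantities that could be called the treatment effect, and they answer different questions.

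- **Group main effect.** If baseline is a response visit, this term averages in a visit at which nobody has been treated.
- **Omnibus interaction.** It asks only whether the arm difference varies over time. It has no direction and gives no single effect size.
- **Contrast at one visit, or averaged over post-baseline visits.** This gives a signed estimate, but its precision depends on whether the baseline score is used as a covariate, subtracted, or ignored.

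At stake are which effect size and interval go forward to planning a full-scale trial, how precise that interval is with 10 men per arm, and what number the Bonferroni correction divides by.

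**Working it through.** The documents give no power, effect size, SD, correlation or alpha, so there is no stated figure to reproduce.

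**Inputs from the documents.** 20 men randomised 1:1, so n = 10 per arm; five visits for scores and Doppler (baseline, weeks 4, 8, 13, 24); MRI at baseline and end of study. (The recruitment target of 24 elsewhere in Section 9 is a separate matter.)

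**Assumptions.** Two-sided 0.05, normal outcome with SD 1, equal correlation ρ between any two visits, true effect d = 1 SD, no dropout.

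**Step 1: dilution if baseline is a response visit.**
- Constant effect: (0 + d + d + d + d)/5 = 0.8d.
- Effect growing as 0, 1/3, 2/3, 1, 1: 3d/5 = 0.6d over five visits, against 3d/4 = 0.75d over the four post-baseline visits.
- MRI with two visits: (0 + d)/2 = 0.5d.

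**Step 2: standard errors and power at ρ = 0.5, constant effect.**

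| Contrast | SE formula | SE | Effect/SE | Power |
|---|---|---|---|---|
| Group term, five visits | √(2·[(1+4ρ)/5]/10) | √0.120 = 0.346 | 0.8/0.346 = 2.31 | 0.59 |
| Week 13, unadjusted | √(2/10) | √0.200 = 0.447 | 2.24 | 0.56 |
| Week 13, change | √(2·2(1−ρ)/10) | √0.200 = 0.447 | 2.24 | 0.56 |
| Week 13, baseline-adjusted | √(2(1−ρ²)/10) | √0.150 = 0.387 | 2.58 | 0.66 |
| Mean of weeks 4–24, unadjusted | √(2·[(1+3ρ)/4]/10) | √0.125 = 0.354 | 2.83 | 0.76 |
| Mean of weeks 4–24, adjusted | √(2·[(1+3ρ)/4 − ρ²]/10) | √0.075 = 0.274 | 3.65 | 0.91 |

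Unadjusted powers use the t distribution with 18 df. Adjusted powers are simulated (20,000 trials, 17 df), so they include the cost of estimating the baseline slope. The 4-df interaction has power of about 0.58.

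Of the gap from 0.59 to 0.91, dropping the pre-treatment visit accounts for 0.76 − 0.59 = 0.17 and baseline adjustment for 0.91 − 0.76 = 0.15. For the growing effect the corresponding powers are 0.37, 0.52 and about 0.71.

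**Step 3: change score against adjustment.** The SE ratio is √(2(1−ρ)/(1−ρ²)) = √(2/(1+ρ)), which exceeds 1 for every ρ below 1. At week 13 the SEs for change and adjusted are 0.529 and 0.427 at ρ = 0.3, and 0.346 and 0.319 at ρ = 0.7. The unadjusted SE is 0.447 throughout.

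**Step 4: disagreement between terms.** With the growing effect at ρ = 0.5, the interaction and the adjusted week-13 contrast reach different verdicts in 32% of simulated trials; the group term and week 13 do so in 43%.

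**Step 5: error rate with no effect.** Take six terms for one outcome: the group term, the interaction and four adjusted visit contrasts.
- Each read at 0.05: at least one is significant in about 0.21 of trials.
- Bonferroni over all six: 0.040 to 0.044.
- Divisor 2 while six are read: about 0.12.

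**Step 6: the divisor.** One contrast for each of two scores gives 2; four visits for each gives 8. Adjusted week-13 power at ρ = 0.5 is 0.53 with divisor 2 and 0.31 with divisor 8.

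**The case against.** The strongest reply is that this is a feasibility study. Its main analytic aims are adherence, retention and guidance on method. No go/no-go rule hangs on a symptom-score p-value, and effect sizes are to be read cautiously beside clinical significance and prior data. That stands and limits the priority. It does not remove the gap: the plan still commits to tests, corrected p-values and an interval, and that interval must come from some contrast.

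Three stronger readings are tempting, and the documents do not support them.

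- *The treatment test is a diluted group main effect.* The plan does not say that baseline is a response row or that the group term is the test. Requiring a baseline and at least one later value fits a covariate or a change score equally well. With baseline as a covariate there is no dilution.
- *The false-positive rate is about four times nominal.* The 0.21 figure ignores the plan's own Bonferroni correction. Inflation arises only if more terms are read than the divisor covers.
- *The average over weeks 4 to 24 is the right contrast.* Section 9 also speaks of evaluation at baseline and end of study, and of sensitivity to change. Aim 2 concerns early recovery, so an arm difference that later fades is plausible. The choice of time point is a trade-off for the sponsor.

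It is also fair to say that the power figures are illustrative: the plan itself expects skewed outcomes with unequal variances.

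**Conclusion.** The concern holds in this limited form. No contrast, visit, role for baseline or Bonferroni family is named, and the baseline score, which is collected anyway, is not listed as a covariate. The concrete gain is precision. At ρ = 0.5 and a 1 SD effect, baseline adjustment raises week-13 power from 0.56 to 0.66 and, for a constant effect, post-baseline-mean power from 0.76 to 0.91. The loss from a five-visit group term (0.8d, power 0.59) is conditional on baseline being modelled as a response. These sizes rest on normality, equal correlation, 10 per arm and an assumed 1 SD effect. The direction of the precision result against change scores does not depend on the value of ρ below 1, although at 10 per arm estimating the slope takes back a little of it. Priority is low to moderate.

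**What to change.** In Section 9, keep the mixed model and Kenward-Roger, and add wording to this effect:

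> The baseline score enters as a covariate, not as a response. A group main effect averaged over the pre-treatment visit is not used as the treatment test. For each primary symptom score (ICIQ, IIEF-5) the treatment effect is one baseline-adjusted between-arm contrast [sponsor to choose: week 13, or the mean of weeks 4, 8, 13 and 24], fixed before unblinding. This contrast supplies the effect size and 95% confidence interval. The Bonferroni divisor equals the number of contrasts tested. Other visits and the group-by-time interaction are supportive.

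With one contrast per score the divisor is 2. Doppler, MRI and mediation analyses can stay as planned, labelled preliminary.

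The cost is wording only: no patients, visits or data. The downside is that a single contrast loses power if the effect follows another time course. For a 1 SD effect at weeks 13 and 24 only, at ρ = 0.5, power is 0.39 for the adjusted mean, 0.66 for week 13 and 0.77 for the interaction. Reporting the other visits as supportive keeps such a pattern visible.

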Patient Recruitment: Our co-investigator, [name] will recruit patients from her urology clinic men over 50 years old who are enrolled for prostate surgery (n=20). After recruitment, 20 male patients will be assigned 1:1 to either age-matched control (G1; sham TPMS) or age-matched intervention (G2; TPMS) groups using computer-generated randomization, and baseline parameters (continence, sexual functions-using standadized questionnaires (please see attachments for reference), PRM, ICM and penile morphology- by MRI, blood flow- using laser Doppler measurement) will be established. All patients will be instructed ([name]) to perform standard of care pelvic floor exercise for the duration of the study. Patients will under go three month TPMS treatment every week (2-visits per week from 0-12 weeks as shown in Figure) starting when she feels the patient is ready for this treatment (after catheter removal). Patients will be evaluated (symptom score, MRI and blood flow) at baseline and at the end of the study (timeline attached). All enrolled patients will undergo TPMS treatment in addition to standard clinical- pelvic floor exercise. The study will be conducted after removal of the in dwelling catheter on patients who: had robotic assisted laparoscopic radical prostatectomy and have no evidence of metastasis and postoperative PSA < 0.2. The TPMS operator will not be blided but those analyzing the IIEF, IQIC scores, and evaluating Doppler blood flow and MRI findings will be blinded to the assignment.

Impact of COVID-19 Pandemic: Due to on-going COVID-19 pandemic, proposed timeline may be impacted due to the restrictions on human research. The scheduling for this research study will be based on availability of SCI suite for exclusive research study use when there are no other patients at that time. Research study patient will be the only patient in the suite at that time of the research study. All facility mandated santization and social distancing protocols will be strictly implemented and followed.

TPMS Treatment: Magnetic stimulation device MagVentrure's R30 (FDA approved for peripheral stimulation) that targets pelvic floor muscles will be used. We propose 10 Hz (for blood flow stimulation) and 30 Hz (for pelvic muscle strengthening), in an 8 seconds on- 4 seconds off

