Feasibility Outcomes: We will estimate: 1) Numbers of potentially eligible patients, number invited, number attending a pre-operative assessment clinic and consent rates (target recruitment is 24 or 3 participants per month over an initial 8-month recruitment period). 2) Patient concerns about the proposed therapy sessions/week and study duration. 3) Feasibility of recruiting in other clinics in which staff are interested in participating in a future main trial. 4) Retention, acceptability rates including response to treatment, questionnaires and imaging. 5) Intervention fidelity and adherence using study coordinator-completed case responses. 6) Determining the sexual function and continence improvement by assessing and comparing sensitivity to change. 7) Participant satisfaction with the interventions on a rating (Likert) scale. 8) Participant confidence to undergo a longer duration TPMS study. 9) Identification of barriers and enablers to adherence. 10) Establishment of outcome measures that best reflects the participants' rehabilitation goals.

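### The Bonferroni correction is valid, but Holm's step-down procedure gives the same family-wise error guarantee and never rejects less; switching is an optional and usually small gain

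*Combined protocol and SAP*

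**What the plan says.** The multiplicity method is one sentence in Section 9, Data Analysis & Interpretation: "We will adjust pvalues for multiple testing using a Bonferroni correction". It follows a sentence naming analysis of variance for the hypothesis test and precedes the mixed-model description. The plan does not say which tests are corrected together, how many there are, or at what alpha.

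Several outcomes could fall under the correction. Section 9.8 says: "Primary symptom scores will be assessed using International Index of Erectile Function (IIEF-5) and International Consultation of Incontinence Questionnaire (ICIQ) symptom scores". Section 9 adds Doppler blood flow and MRI, and has scores and blood flow measured at baseline and "at weeks 4,8, 13, 24 after starting TPMS".

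On size, Section 9 (Patient Recruitment) says "20 male patients will be assigned 1:1 to either age-matched control (G1; sham TPMS", with an active-stimulation arm as the other group. Feasibility Outcomes in the same section says "target recruitment is 24 or 3 participants per month over an initial 8-month recruitment period". On attrition: "we expect a dropout rate of <10% after baseline assessment".

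The same analysis text treats every analysis as preliminary, directs the work mainly to adherence, retention and changes of method, and reads the primary effect size "in the context of the 95% confidence interval that surrounds it".

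**The concern.** Bonferroni tests every hypothesis at alpha divided by the number of tests. Holm does so only for the smallest p-value and relaxes the threshold for each later one, with no further assumption. If the purpose is to decide which of several outcomes differ between arms, Bonferroni can miss outcomes that Holm would have declared, with the same bound on false positives.

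With about 10 men per arm there is little sensitivity to spare. The study also aims to learn which outcome measures respond to change (Section 9, Feasibility Outcomes), which is an outcome-by-outcome question. At stake is some power for the second and later outcomes, not the validity of the analysis.

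**Working it through.** **Inputs**

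- From the documents: Bonferroni on p-values; 20 patients at 1:1, so 20/2 = 10 per arm.
- Assumed, because the documents do not say: two-sided 5% (suggested by the 95% interval); four outcomes (two scores, blood flow, MRI), one test each; correlation 0.3; standardised effects d of 0.5, 0.8 and 1.3; normal data and two-sample t-tests with 18 degrees of freedom standing in for the mixed model.
- The plan's sample size of 20 comes with no alpha, power, effect size or SD, so there is no figure of its own to reproduce.

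**Step 1: the two rules.** With m tests, Bonferroni rejects any p at or below 0.05/m. Holm orders the p-values and compares the i-th smallest with 0.05/(m − i + 1), stopping at the first failure. For m = 4, Bonferroni uses 0.0125 throughout; Holm uses 0.0125, 0.0167, 0.025 and 0.05.

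**Step 2: error control.** Suppose m0 hypotheses are truly null. When Holm first rejects a true null, at most m − m0 hypotheses have already been rejected, so the threshold then is at most 0.05/m0. The chance that any of the m0 null p-values falls that low is at most m0 × 0.05/m0 = 0.05, whatever the correlation. In simulation with every hypothesis null (m = 2, 4, 8; correlation 0 and 0.5), the error rate was the same for both methods, 0.042 to 0.049. With some effects real, Holm uses more of the allowance but stays within it: with d = 0.8 on two of four outcomes and correlation 0.5, the chance of a false rejection was 2.4% under Bonferroni and 3.1% under Holm.

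**Step 3: what cannot change.** Holm's first threshold is Bonferroni's. The two therefore reject at least one hypothesis in exactly the same trials. In the four-outcome case with d = 1.3 on all and correlation 0.3, that chance is 91.1% under both.

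**Step 4: what can change.** Simulated power per truly affected outcome, m = 4, correlation 0.3, 10 per arm:

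| True effects | Bonferroni | Holm | Gain (points) |
|---|---|---|---|
| d = 0.5 on all four | 7.0% | 7.8% | 0.8 |
| d = 0.8 on all four | 19.6% | 23.3% | 3.7 |
| d = 1.3 on all four | 56.4% | 67.7% | 11.3 |
| d = 1.3 on one of four | 56.2% | 56.3% | 0.1 |

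Cross-check of the Bonferroni column by the noncentral t with noncentrality d × √(10/2): at two-sided 0.0125 the critical t is 2.775. For d = 0.8 the noncentrality is 1.789 and power is 19.5%; for d = 1.3 it is 2.907 and power is 56.2%. These agree with the simulation. A single unadjusted test at d = 0.8 (critical t 2.101) has only 39.5% power, so sample size is the main limit under either method.

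**Step 5: other sizes** (d = 0.8 on all outcomes, correlation 0.5):

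| Per arm | Tests | Bonferroni | Holm |
|---|---|---|---|
| 10 | 2 | 28.2% | 32.0% |
| 10 | 4 | 19.5% | 23.8% |
| 10 | 8 (two scores × four visits) | 13.0% | 16.1% |
| 9 (10% dropout from 20) | 2 | 24.9% | 28.3% |
| 12 (if 24 are recruited) | 2 | 34.5% | 39.0% |

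The conclusion does not depend on whether 20 or 24 applies.

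**The case against.** The strongest reply is that nothing here is wrong. Bonferroni is valid and pre-specified, the tests are declared preliminary, and no stated decision turns on an adjusted p-value: outcome measures are to be judged by sensitivity to change and by participants' rehabilitation goals. This stands, and it is why the point is optional.

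A second reply is that Bonferroni has simple matching simultaneous confidence intervals and Holm has none equally simple. That is true, but the plan corrects p-values and asks only for an ordinary 95% interval around the primary effect size. The swap leaves that interval alone.

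A third reply is that the family is undefined, so neither method can be applied as written. That also stands. The four-outcome family used above is an illustration; the corrected tests might equally be visit contrasts within an outcome. Changing the method does not close that gap.

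Three stronger readings are tempting and unsupported:

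- A reader might infer that Bonferroni throws away much of the study's power. The gain ranges from 0.1 to 11.3 points in the illustration, and its upper end needs a very large effect on every outcome, which the documents do not claim.
- A reader might infer that Bonferroni favours a false finding of no signal for the study overall. It cannot, because the chance of at least one rejection is identical.
- A reader might infer that Holm gains most when outcomes are correlated. With four outcomes at d = 1.3, the per-outcome gain shrinks from about 12 to about 8 points as correlation rises from 0 to 0.9. At d = 0.8 it grows, but only from 2.5 to 4.9 points. The plan states no correlation and lists it as something to be examined.

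**Conclusion.** The point holds as an optional refinement. For reject-or-not decisions on a fixed set of tests, Holm has the same 5% family-wise guarantee as Bonferroni under any dependence and keeps all its rejections. That part rests on no assumption beyond valid p-values.

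The size of the benefit does rest on assumptions: effect size, number of tests, correlation, alpha and normality, none of which the documents settle. With modest effects, or effects on few outcomes, the gain is between almost nothing and about 4 points per affected outcome. It reaches about 11 points only when every outcome has an effect near 1.3 SD. No feasibility conclusion depends on it.

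**What to change.** In Section 9, Data Analysis & Interpretation, replace the Bonferroni correction with the Holm step-down procedure, applied to whatever family of between-arm tests the sponsor had in mind for Bonferroni. Leave the 95% confidence interval for the primary effect size unchanged.

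The swap itself is a change of one term, with no loss of error control, no new data and no extra patients. Its small cost is the lack of simple matching simultaneous intervals, which the plan does not request. The sponsor will still need to state which tests form the family and at what alpha before either method can be run; that choice belongs to the sponsor and is not prescribed here.

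### The plan promises intent-to-treat, but its only stated analysis set requires a baseline and a post-baseline evaluation, which is modified intent-to-treat

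*Combined protocol and SAP*

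**What the plan says.** All of this is in the combined protocol and SAP, Section 9 (Design and Methods).

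- **Principle.** Near the end of Data Analysis & Interpretation: "Primary outcomes will be tested using an intent-to-treat framework".
- **Model.** The same text chooses a mixed effect model and gives as a reason that it can take in patients with missing data or early termination without imputation.
- **Set.** Shortly after, and just before the mediation tests: "Data will be analyzed from all randomized subjects for whom we have a baseline assessment and at least one post-baseline evaluation". No other analysis population is defined.
- **Timing.** TPMS Treatment schedules questionnaires and Doppler at "baseline (before starting TPMS), and at weeks 4,8, 13, 24 after starting TPMS".
- **Size.** Patient Recruitment states: "After recruitment, 20 male patients will be assigned 1:1 to either age-matched control".
- **Focus.** The analysis text says: "The primary aims of our data analytic strategy will be directed toward the adherence, retention and any guidance to inform modification of our method". Retention and adherence are items 4 and 5 of Feasibility Outcomes, where neither has a denominator.
- **Dropout.** The stated expectation is: "we expect a dropout rate of <10% after baseline assessment".

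**The concern.** Intent-to-treat means that patients are analysed as randomised, whatever happens to them afterwards. A rule that requires a later evaluation selects on something that happens after randomisation. Here it removes the patients who withdraw earliest, although the model was chosen partly for its ability to keep such patients.

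Such losses are foreseeable. Consent is obtained before surgery (Section 12.1d). Patient Recruitment describes randomisation before it describes baseline measurement. Treatment waits for catheter removal and the clinician's judgement that the patient is ready, and the study is conducted in patients who meet a postoperative PSA condition and have no metastasis. The exact time of randomisation relative to surgery is not stated. If it comes first, a patient could be randomised and never start.

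Two things are at stake. A reader of the results would be told that the analysis was intent-to-treat when it was not, and the group-by-time contrast would carry an avoidable selection effect.

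**Working it through.** **1. The statements side by side.** The principle covers primary outcomes. Data Analysis & Interpretation does not define these; Section 9.8 names the IIEF-5 and ICIQ as the primary symptom scores. The set rule covers the data that enter the mixed model. For those scores the two cannot both hold once a randomised patient lacks a baseline or any later evaluation. Nothing in the plan reconciles them.

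**2. How long a patient is at risk of exclusion.** Planned visits: 2 per week × 12 weeks = 24. Visits due by the first post-baseline assessment: 2 × 4 = 8. A patient could therefore attend up to 8 of 24 visits and still be excluded.

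**3. Effect on the mixed model.** An excluded patient with only a baseline has no follow-up value under either approach, so only the baseline information changes. With 20 randomised 1:1 there are 10 per arm. Suppose one patient in an arm has only a baseline, that this value differs by *d* from the mean of the other nine, and that those nine have complete data.

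- Keeping the patient moves the arm's baseline mean by *d*/10.
- In a model with baseline as a response and unconstrained means, the estimated change from baseline then moves by (1 − β) × *d*/10 in absolute value, where β is the slope of follow-up on baseline.
- For β between 0 and 1 (an assumption), that is at most *d*/10. Two such patients in one arm, each differing by *d* from the other eight, give at most 2*d*/10 = *d*/5.

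The documents give no SD or within-patient correlation, so this cannot be turned into score points. It is modest, and it is zero with no early loss.

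**4. Feasibility rates, only if the same set were applied to them.** Retention over all randomised = retained / 20. Over the restricted set = retained / (20 − early losses). The loss counts are assumptions.

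| Lost before week 4 | Lost later | All 20 randomised | Restricted set | Difference (points) |
|---|---|---|---|---|
| 0 | 2 | 18/20 = 90.0% | 18/20 = 90.0% | 0 |
| 1 | 0 | 19/20 = 95.0% | 19/19 = 100% | 5.0 |
| 1 | 3 | 16/20 = 80.0% | 16/19 = 84.2% | 4.2 |
| 2 | 0 | 18/20 = 90.0% | 18/18 = 100% | 10.0 |
| 2 | 1 | 17/20 = 85.0% | 17/18 = 94.4% | 9.4 |
| 4 | 1 | 15/20 = 75.0% | 15/16 = 93.8% | 18.8 |

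Each early loss adds about 4 to 5 points. The uncertainty is wide in any case: the Clopper-Pearson 95% interval for 17/20 is 62.1% to 96.8%, and for 17/18 it is 72.7% to 99.9%.

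Adherence behaves in the same way. Take 2 early leavers who attend between 0 and 8 visits, with everyone else attending all 24. Over all randomised it is (18 × 24 + 0)/480 = 90.0% to (18 × 24 + 16)/480 = 93.3%. Over the restricted set it is 432/432 = 100%.

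**5. Sample size.** Feasibility Outcomes gives a different number: "target recruitment is 24 or 3 participants per month over an initial 8-month recruitment period". If 24 were randomised, one early loss would give 23/24 = 95.8% against 23/23 = 100%, a difference of 4.2 points.

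**The case against.** A reader might infer that retention and adherence, the main focus of the study, will be overstated, and that a retention failure could pass as a success. The documents do not support this, for four reasons.

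- By position, the set sentence belongs to the mixed model. It follows the small-sample degrees-of-freedom correction, and the next sentence refers to the same model.
- Feasibility Outcomes is a separate list that starts from eligible and invited patients. Adherence comes from coordinator-completed records, so it needs no week-4 assessment.
- Dropout rates and missing-data patterns are to be evaluated as preliminary analyses, and differences between dropouts and completers are to be explored.
- The plan's dropout expectation counts from baseline. If all 20 have a baseline and 3 leave, 2 of them before week 4, dropout is 3/20 = 15%. That visibly misses the expectation of under 10%, which allows at most 1 of 20. The 17/18 in the table uses a denominator that the plan never states.

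It can also be said that patients with only a baseline add little to a group-by-time contrast, and that the plan calls all its analyses preliminary.

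These arguments limit the point to the mixed model and to a modest size. They do not remove the conflict between the promised framework and the stated set. The set sentence is also worded generally and no other population is defined, so a clarification about the feasibility rates is still worth making.

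**Conclusion.** The point holds for the analysis set. The plan states intent-to-treat, but the set it specifies is modified intent-to-treat. The likely effect on the mixed-model estimate is small, and zero if nobody is lost before week 4.

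Overstated retention or adherence is not established. It would follow only if the restricted set were used as the denominator, at about 4 to 5 points per early loss with 20 randomised. The documents neither say that it will be nor say that all randomised patients will be used. The missing denominator is a gap in detail, not a demonstrated bias.

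The figures assume 20 randomised and the illustrative loss counts shown.

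**What to change.** 1. Remove the requirement for a post-baseline evaluation. Fit the mixed model with baseline as one of the responses, so that every randomised patient with a baseline is included. If the present rule is kept, call the set modified intent-to-treat wherever results are reported.
2. Report by arm the number randomised without usable data, separating those with no baseline from those with a baseline only. A patient with no measurement at all cannot inform the model under either approach, so this count is needed even after the first change.
3. As a clarification, state that retention, adherence and acceptability are calculated over all randomised patients.

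This takes a few sentences and no new data. The only downside is that the retention figure may look less favourable.
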